## 1. Introduction

### 1.1. Study Abstract

In the United States, preterm birth (PTB) at < 37 weeks is the greatest contributor to neonatal death. Late PTBs between 34 and 36 weeks comprise over 70% of all PTB. Compared to term neonates, those born late preterm are more likely to have respiratory distress, hypothermia, and poor feeding. This increases hospital stay, NICU admissions, and hospital readmissions. In a randomized clinical trial, maternal betamethasone (BMZ) given to women at risk of delivery in the late preterm period lowered neonatal respiratory complications, but increased neonatal hypoglycemia, compared to placebo. Previous studies have demonstrated an association between antenatal BMZ and maternal hyperglycemia as well as antenatal BMZ and fetal hyperinsulinemia. Thus, neonatal hypoglycemia observed after antenatal BMZ for threatened late PTB is likely due to transient steroid-induced maternal hyperglycemia.

This protocol describes a multisite randomized controlled trial to define the fetal metabolic and hormonal response to late preterm BMZ exposure, and the effect of maternal glucose control on fetal metabolic and hormone levels.

### 1.2. Primary Hypothesis

BMZ exposure in the late preterm period is associated with fetal hyperinsulinemia as measured by umbilical cord blood C-peptide level. Compared to usual care (no glucose screening), regular screening for and treatment of maternal hyperglycemia following antenatal BMZ administration in pregnancies at risk for late preterm birth will result in lower umbilical cord blood C-peptide level.

### 1.3. Purpose of the Study Protocol

This protocol describes the background, design and organization of the randomized clinical trial and may be viewed as a written agreement among the study investigators. The Data and Safety Monitoring Board (DSMB) will review the protocol. Before recruitment begins, the protocol will be approved by the Institutional Review Board (IRB) of each clinical center. Any changes to the protocol during the study period require the approval of the IRBs; major changes also require the approval of the DSMB.

## 2. Background

### 2.1. Incidence and Complications of Late Preterm Birth

Preterm birth is the greatest contributor to neonatal death in the United States. In 2013, preterm births made up 11.4% of all live births and over 70% of all preterm births were between 34 weeks 0 days and 36 weeks 6 days gestation. Based on a consensus statement of the NICHD workshop entitled “Optimizing Care and Outcome of the Near-Term Pregnancy and the Near-Term Newborn Infant,” neonates born during this time period are considered to be “late preterm” neonates.

While the etiology for late preterm birth can vary from spontaneous labor or premature rupture of membranes to iatrogenic delivery for maternal or fetal indications, studies have shown that regardless of indication, neonates born during the late preterm period are at increased risk for complications compared to those born at term. In a study of 21,771 late preterm births, specific neonatal morbidities such as ventilator-treated respiratory distress, transient tachypnea of the newborn, grade 1 or 2 intraventricular hemorrhage, sepsis, and

hyperbilirubinemia were all more common in late preterm compared to term neonates. Other studies have also shown an increased risk for problems with temperature regulation and difficulty feeding with resulting hypoglycemia. While mortality remains rare in the late preterm period, neonatal death after birth at 34, 35, and 36 weeks is still higher compared to death after delivery at term.

## 2.2. Effect of Antenatal Corticosteroids on Neonatal Morbidity

In 2016 an important step toward reducing respiratory morbidity in neonates born in the late preterm period occurred. A study of 2827 late preterm pregnancies showed a significant reduction in respiratory complications among neonates exposed to BMZ in utero compared to placebo (11.6 v 14.4%,  $p=0.02$ ), however, neonatal hypoglycemia was more common in the BMZ compared to placebo group (24% vs 15%,  $p<0.001$ ). There was no significant reduction in NICU admission (41.8 v 44.9%,  $p=0.09$ ), suggesting that there is potential for additional improvement in late preterm neonatal outcomes. Other studies have also demonstrated an increase in neonatal hypoglycemia after exposure to BMZ, although the mechanism has not yet been studied.

## 2.3. Rationale for Neonatal Hypoglycemia after Antenatal Corticosteroids

Previous studies have shown that antenatal corticosteroids are associated with transient but significant maternal hyperglycemia. Almost all non-diabetic pregnant women who receive antenatal BMZ experience at least 1 capillary blood glucose (CBG) level above 140mg/dL, which persists for 3-4 days for most women. Current clinical practice for non-diabetic women who receive BMZ does not include any CBG monitoring, and thus the opportunity to correct any maternal hyperglycemia is missed. While the neonatal effects of maternal hyperglycemia have not been studied in this context, umbilical cord blood studies have demonstrated increased fetal C-peptide levels after antenatal BMZ exposure. This BMZ-induced fetal hyperinsulinemia suggests that the neonatal effects after BMZ may be similar to those seen in neonates of diabetic mothers with hyperglycemia.

Maternal hyperglycemia, even if transient, can lead to fetal hyperglycemia with subsequent fetal insulin production, placing the neonate at risk for hypoglycemia at birth. BMZ acts on multiple maternal tissues to increase maternal glucose: 1) BMZ decreases pancreatic insulin release, 2) BMZ increases insulin resistance in the liver, increasing glucose production, and 3) BMZ increases insulin resistance in the muscle and fat cells, decreasing glucose uptake. Elevated circulating maternal glucose crosses the placenta and subsequently stimulates the fetal pancreas to produce insulin. Neonates delivered during this transient period of hyperinsulinemia are then at risk for hypoglycemia at birth. Fundamental gaps in understanding the adverse maternal and fetal metabolic effects of antenatal late preterm steroids have limited our ability to achieve better neonatal outcomes.

## 2.4. Rationale for a Randomized Clinical Trial

Late preterm births at 34 weeks 0 days – 36 weeks 6 days gestation comprise over 70% of all US preterm births. In the US annually over 300,000 neonates are born in the late preterm period. While a recent study of 2827 late preterm pregnancies showed a significant reduction in respiratory complications of neonates born to mothers treated with BMZ compared to placebo, this exposure was also associated with an increase in neonatal hypoglycemia. The Society of Maternal-Fetal Medicine (SMFM) Statement in August 2016 acknowledged that “concern has been raised about the potential increased risks associated with neonatal hypoglycemia” following antenatal BMZ. SMFM reassured both obstetricians and neonatologists that “these [risks] should be minimized by the utilization of routine [postnatal] testing for all late preterm newborns, as advocated by the Committee on Fetus and Newborn of the American Academy of Pediatrics.

Our proposal is innovative because we are challenging the current dogma regarding the management of non-diabetic women receiving antenatal BMZ in the late preterm period. The current approach of disregarding maternal hyperglycemia potentially diminishes neonatal benefits of antenatal BMZ. Despite the impact of late preterm BMZ on neonatal respiratory morbidity, the best strategy to optimize overall neonatal outcome, including preventing hypoglycemia, is unknown. We contend that neonatal hypoglycemia associated with antenatal BMZ in the late preterm period can be prevented, just like that seen in diabetic mothers. Our proposal to test maternal glucose in non-diabetic women who receive BMZ in the late preterm period addresses the challenge of understanding the metabolic effects of antenatal BMZ. We expect to find that treatment of BMZ-induced maternal hyperglycemia decreases the frequency of neonatal hypoglycemia after birth. *Completion of our study lays the foundation for a future multicenter trial with potential to change clinical practice for treatment of women with threatened late PTB.*

### 3. Study Design

#### 3.1. Primary Research Question

This study will address the following primary research questions:

Aim 1: What is the association between late preterm steroid exposure and fetal C-peptide levels, compared to no steroid exposure?

Aim 2: What is the effect of screening for and treatment of BMZ-induced maternal hyperglycemia on fetal C-peptide levels.

#### 3.2. Secondary Research Questions

Secondary research questions this study will address are:

- What are other fetal metabolic and hormonal effects of late preterm steroid exposure, compared to no steroid exposure?
- What are other fetal metabolic and hormonal effects of screening for and treatment of BMZ-induced maternal hyperglycemia, compared to usual care (no glycemic control)?
- What is the prevalence of neonatal hypoglycemia in the steroid exposed vs unexposed groups? Does screening for and treatment of steroid-induced maternal hyperglycemia decrease the prevalence of neonatal hypoglycemia?
- What is the degree and duration of neonatal hypoglycemia?
- Does screening for and treatment of steroid-induced maternal hyperglycemia decrease the prevalence of NICU admission?
- What is the effect of timing of delivery on fetal metabolic and hormonal levels?

#### 3.3. Design Summary

This proposal includes use a retrospective cohort of 75 mother-neonate dyads and umbilical cord samples collected during the Maternal Oral Therapy to Reduce Obstetric Risk (MOTOR) trial, as well as a prospective cohort of 144 mother-neonate dyads prospectively enrolled in our randomized clinical trial.

Women who had enrolled in the MOTOR trial, now completed, will serve as unexposed controls for this new proposal, as antenatal BMZ was reserved for threatened PTB less than 34 weeks' gestation at the time the trial was conducted. The MOTOR trial was a randomized, blinded trial of 1,760 pregnant women with periodontal disease to measure the impact of periodontal treatment during pregnancy on maternal and neonatal outcomes. Of these, there are approximately 1500 stored umbilical cord blood specimens from otherwise healthy, non-diabetic women, 5% of whom delivered between 34 weeks 0 days and 36 weeks 6 days. We have

been granted access to use 75 umbilical cord blood samples which meet inclusion criteria as unexposed late PTB controls to compare to the samples we collect in our randomized clinical trial.

For this randomized clinical trial, we will enroll 144 non-diabetic women with singleton pregnancies who are receiving betamethasone between 34 weeks 0 days and 36 weeks 5 days in anticipation of late preterm delivery. Eligible, consenting women will be randomized to one of two management schemes:

1. Intervention group: maternal capillary blood glucose (CBG) screening with treatment of hyperglycemia with insulin per existing institution protocol for diabetic women. Guidelines based on the existing UNC-CH algorithm for treatment of diabetic women are demonstrated Tables 1 and 2 below.

Table 5 Maternal insulin algorithm if NPO	
CBG q 1-2hr	IV Regular Insulin
<110mg/dL	Stop insulin infusion
111-140mg/dL	1 U/hr
141-180mg/dL	1.5 U/hr
181-220mg/dL	2 U/hr
>220mg/dL	2.5 U/hr & titrate

Table 6 Maternal insulin sliding scale if eating general diet	
CBG fasting and 1hr post-prandial	SQ Insulin
<110 mg/dL	0 units
111-140 mg/dL	1 unit if fasting BG*
141-180 mg/dL	1 unit
181-220 mg/dL	2 units
>220 mg/dL	4 units & consider infusion

2. Control group: usual care with no CBG screening or treatment as is current protocol at UNC-CH as well as other participating institutions

### 3.4. Eligibility Criteria

#### 3.4.1. Inclusion Criteria

1. Singleton Pregnancy. A multiple gestation reduced to singleton (either spontaneously or therapeutically) before 14 weeks 0 days by project gestational age (see Section 3.4.2 below) is acceptable.
2. Gestational age at time of 1st dose of betamethasone administration between 34 weeks 0 days and 36 weeks 5 days confirmed by study criteria (see Section 3.4.2 below)
3. Receiving or already received betamethasone for clinical indications within 6 hours of randomization.
4. Likelihood of delivery in the late preterm period (any one of the following):
  - a. Membrane rupture as defined by visible leakage of amniotic fluid from the cervix, Positive AmniSure test, or the presence of any two of the following:
    - i. Pooling of fluid in the vaginal vault
    - ii. Positive nitrazine test
    - iii. Ferning of vaginal fluid
  - b. Preterm labor with intact membranes. Preterm labor is defined as at least 6 regular uterine contractions in 60 minutes and at least one of the following:
    - i. Cervix greater than or equal to 3cm dilated
    - ii. At least 75% effaced
  - c. Maternal or fetal indication for delivery (either by induction of labor or cesarean section) at less than 37 weeks' gestation (e.g. placenta accreta).
  - d. Delivery expected in no less than 12 hours and no more than 7 days, as deemed necessary by the provider. An induction must be scheduled to start by 36 weeks 5 days at the latest, whereas a cesarean delivery must be scheduled by 36 weeks 6 days at the latest.

5. Planned inpatient management until delivery.

3.4.2. Gestational Age Determination

Gestational age is determined in the following manner, and is denoted “project gestational age”. The “project EDD”, which is based on the project gestational age, cannot be revised once a determination has been made.

3.4.2.1. Spontaneous Pregnancies

This algorithm is also applicable to pregnancies where ovulation induction or artificial insemination was performed and is based upon a comparison of LMP and gestational age as assessed by the earliest dating ultrasound. If a patient has never received an ultrasound at the time of screening, she is automatically ineligible.

To qualify as the earliest dating ultrasound:

- If a very early ultrasound, it must be based on a fetal pole with a crown-rump length
- Gestational age cannot be determined by gestational sac measurement
- There must be a report or an image showing the ultrasound measurements or a note in the patient’s chart documenting the date of the ultrasound and the ultrasound measurements or exact EDC or GA.

The first day of the last menstrual period (LMP) is determined, and a judgment made as to whether the patient has a “sure” LMP date.

1. If the LMP date is unsure, the ultrasound measurements obtained at the patient’s first dating ultrasound examination are used to determine the project gestational age (Table 1). This ultrasound must have been performed before the time of screening.
2. If the LMP date is sure, project gestational age is determined by a comparison between the gestational age by LMP and by the earliest dating ultrasound. This ultrasound must have been performed before the time of screening.
  - a. If the earliest dating ultrasound confirms the gestational age by LMP within the number of days specified in Table 1 below, the LMP-derived gestational age is used to determine the project gestational age.
  - b. If the ultrasound determined gestational age does not confirm the LMP generated gestational age within the number of days specified in Table 1, the ultrasound is used to determine the project gestational age.

Gestational age at first ultrasound by LMP	Method of measurement	Ultrasound agreement with LMP
≤ 8 6/7 wk 9 0/7 wk to 13 6/7 wk	CRL	More than 5 days More than 7 days
14 0/7 wk to 15 6/7 wk 16 0/7 wk to 21 6/7 wk 22 0/7 wk to 27 6/7 wk ≥ 28 0/7 wk	BPD, HC, AC, FL	More than 7 days More than 10 days More than 14 days More than 21 days

3.4.2.2. In-Vitro Fertilization

One exception to the algorithm above is the case where the patient has undergone in-vitro fertilization (IVF) to achieve pregnancy. If in-vitro fertilization is used (standard IVF, IVF with donor egg, or IVF with ICSI) and

- the embryo is transferred at 3 days of age, the project EDD is 263 days after the date of transfer;
- the embryo is transferred at 5 days of age, the project EDD is 261 days after the date of transfer.

### 3.4.3. Exclusion Criteria

1. Diabetes, pregestational or gestational
2. Any prior antenatal corticosteroid course during the current pregnancy
3. Systemic corticosteroid administration during pregnancy (at least 5mg oral prednisone or its equivalent for at least 3 weeks)
4. Planned outpatient treatment with antenatal corticosteroids
5. Current multiple gestation or multiple gestation reduced to a singleton gestation at or after 14 weeks 0 days by project gestational age either spontaneously or therapeutically
6. Fetal demise, or known major fetal anomaly, including cardiac anomaly and hydrops
7. Maternal contraindication to insulin: history of hypersensitivity reaction to any components of the medication
8. Delivery planned within 12 hours of randomization
9. Delivery planned at or after 37 weeks 0 days gestation
10. Delivery planned outside the E-ALPS Consortium
11. Participation in another interventional study
12. Participation in this trial in a previous pregnancy

### 3.5. Informed Consent Criteria

Written informed consent must be obtained before entry into the study. Full disclosure of the nature and potential risks of participating in the trial is to be made.

Each center will develop its own consent forms according to the requirements of its own institutional review board using the model consent forms in the Appendix. Each center will also develop its own patient research authorization documents, as required by the HIPAA Privacy Rule, following the guidelines of its own institution. A copy of the signed consent form for the study will be provided to the patient.

Women who are not fluent in English will be enrolled by a person fluent in their language. Both verbal and written informed consent and authorization will be obtained in that language; if this is not possible the patient will be excluded.

### 3.6. Randomization Method

The randomization sequence will be prepared in a permuted block design, stratified by study site and gestational age at trial entry (34 weeks 0 days – 34 weeks 6 days and 35 weeks 0 days – 36 weeks 5 days) to assure balance between the two groups with respect to anticipated differences within the patient populations and possible differences in other aspects of patient management. The study statistician will create the randomization scheme, and assignments will be centrally assigned using the Research Electronic Data Capture (REDCap) application. Enrolled subjects will be randomized in a 1:1 ratio to usual care (no maternal glucose screening or treatment) or to study intervention (regular maternal glucose screening and treatment).

The randomization sequence will be generated by a statistician and uploaded into REDCap. This sequence will be unknown by any other study personnel and will be unable to be accessed in REDCap by anyone other than the statistician. As such there is full concealment of randomization group until a patient is screened, meets all eligibility criteria, signs the consent form, and the randomization function in REDCap is utilized to place the subject in the control or intervention group. Once the subject is assigned to a group, this randomization cannot be undone.

## 4. Study Procedures

### 4.1. Screening for Eligibility and Consent

All pregnant women with a singleton pregnancy who are receiving betamethasone between 34 weeks 0 days and 36 weeks 5 days because of anticipated delivery before 37 weeks are potentially eligible for screening. The inclusion/exclusion criteria will be reviewed with each patient's chart. If a patient is eligible, the study will be explained to her and she will be asked to sign the informed consent form.

### 4.2. Randomization

Eligibility will be confirmed just prior to randomization. Subjects will be randomized by central assignments using the Research Electronic Data Capture (REDCap) application prior to or less than 6 hours after betamethasone administration. Once a patient's study identifier has been entered on the randomization log, that patient remains randomized regardless of whether the management protocol in each group (screening and treatment vs usual care) is adhered to.

### 4.3. Baseline Procedures

In addition to information collected for eligibility, project gestational age, and project EDD determination, the following information will be obtained at randomization from a patient interview followed by a review of her medical record:

- Demographic and anthropometric information: age, race, pre-pregnancy weight, current weight, and height
- Social history: marital status, years of education, alcohol use, tobacco use, and other maternal drug use
- Medical/surgical history: pre-existing maternal medical problems such as cardiac disease, asthma, infections, thyroid disorder
- Obstetrical history including value of diabetes testing in this pregnancy (1hr 50g glucose screen and 3hr 100g oral glucose tolerance test) and outcome of all prior pregnancies
- Current pregnancy complications including membrane rupture, preterm labor, bleeding, hypertensive disorders of pregnancy, oligohydramnios, non-reassuring fetal status, etc.

### 4.4. Patient Management and Follow-up

Other than the timing and frequency of maternal glucose screening and recommended thresholds for treatment of hyperglycemia detailed in the study protocol, women will receive standard care as defined by their clinical provider. Women randomized to the intervention arm will undergo screening for and treatment of maternal hyperglycemia until delivery or hospital discharge for a maximum of 5 days following BMZ.

All study neonates will have CBG testing within 2 hours of life. This is standard of care for neonates born at less than 37 weeks. As part of the study protocol, CBG will be measured within 2 hours of life on those neonates who are delivered at or after 37 weeks and 0 days. The remainder of neonatal care will be according to the clinical provider. Umbilical cord blood and placental samples will be collected after delivery to evaluate fetal metabolic status in utero as well as other genetic changes. All study specimens will be labeled with a unique study ID code. Personnel responsible for lab assays will receive the specimens in a coded fashion without any documentation of PHI or study arm.

- Placental biopsies:
  - 15 punch biopsies will be obtained from each placenta using a standard 3mm punch biopsy tool. Biopsies should be obtained 2 cm from the cord insertion site.
  - Three punch biopsy samples will be placed into 5 separate aliquot tubes.
  - 0.5mL AllProtect solution will be placed in 3 of the 5 aliquot tubes
  - The other 2 aliquot tubes will be empty
- Placental portions:
  - 2 placental portions should be removed using sharp dissection (scalpel or scissors). Each portion should measure approximately 0.5 by 0.5 inches and should traverse the complete depth of the placenta.
  - Each placental portion should be placed into a 15mL falcon tube
  - The distance from the cord insertion should be recorded. One portion should be removed 2 cm from the cord insertion. The other should be removed 2 cm from the periphery.

While maternal CBG will only be performed for maximum of 5 days following BMZ, maternal postpartum data will be collected through hospital discharge. Neonatal data will be collected through hospital discharge or until 28 days of life.

#### 4.5. Adverse Event Reporting

Detailed information concerning adverse events will be collected and evaluated throughout the conduct of the protocol. Patients will be questioned in a non-directed manner regarding side effects or symptoms associated with the management plan daily after receipt of betamethasone for maximum of 5 days.

In addition, an Adverse Event Form will be completed for any event that is serious, deemed potentially related to the study, and/or unexpected in nature, severity or frequency. The Adverse Event form will be sent by fax within forty-eight hours to the Primary Investigator. The Primary Investigator will be notified immediately (within 24 hours) of any maternal, fetal, or neonatal deaths. If a death is reported, a copy of the patient’s medical record will be made. Adverse events will be reported to the Data and Safety Monitoring Board (DSMB), and will be considered along with other interim safety data in their deliberations.

The Common Terminology Criteria for Adverse Events (CTCAE) scale will be used to evaluate adverse events in a consistent manner across all sites. Maternal hypoglycemia is a known adverse event which can result from overtreatment with insulin. The following grading scale will be used to define the severity of the adverse event.

Adverse Event	Grade 1 (Mild)	Grade 2 (Moderate)	Grade 3 (Severe, medically significant)	Grade 4 (Life-threatening consequences)	Grade 5 (Death)
Hypoglycemia (mg/dL)	< LLN – 55	< 55 – 40	< 40 – 30	< 30 or seizures	Death

**Subject** stopping rules will include:

- CTCAE grade 4 or 5 hypoglycemia
- Patient requests to withdraw from study

**Study** stopping rules will include:

- CTCAE grade 4 or 5 hypoglycemia in more than 33% of patients receiving intervention
- CTCAE grade 3 hypoglycemia in more than 50% of patients receiving intervention

Other potential reasons for stopping the entire study include: occurrence of any grade 3 (severe) or grade 4 (life-threatening) SAE in 50% percent of subjects that an independent medical monitor and DSMB believe is likely related to active treatment.

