## 5.2. Interim Analysis

The Data and Safety Monitoring Board meets monthly; however, a formal interim analyses for overwhelming efficacy is planned after 50% of recruitment is completed (n=75). For the planned interim analysis, a formal detailed statistical report will be written by [name], Biostatistician including protocol adherence, the primary outcome, and adverse events reported as well as center performance in terms of recruitment, data quality, loss to follow-up and protocol violations.

The main statistical issue relevant to interim analysis is the problem of performing multiple tests of significance on accumulating data. A number of procedures have been developed to handle this situation. For this trial, the group sequential method will be used to control the type I error with the Lan-DeMets spending function and the O’Brien-Fleming type boundary. Assuming that the analysis is conducted at precisely 50%, this implies that the alphas to be used will be 0.003 and 0.049 at the interim and final analyses, respectively. However, this should not preclude the Data and Safety Monitoring Board recommending termination earlier if there is evidence of harm. Pre-specified stopping rules for safety will be developed.

It is recognized that any decision to terminate the study would not be reached solely on statistical grounds but on a number of complex clinical and statistical considerations.

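### The study-level stopping criteria in section 4.5 do not fit their own grading scale: a death is pooled with non-fatal hypoglycemia under a more-than-33% rule, and the general SAE criterion leaves out grade 5

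*Combined protocol and SAP*

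**What the plan says.** Section 4.5 introduces a CTCAE table for maternal hypoglycemia in which grade 4 is a reading below 30 mg/dL or seizures, and grade 5 is death. It then gives three study-level criteria:

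- For the two highest grades, "CTCAE grade 4 or 5 hypoglycemia in more than 33% of patients receiving intervention"
- For the next grade down, "CTCAE grade 3 hypoglycemia in more than 50% of patients receiving intervention"
- As a further potential reason, "occurrence of any grade 3 (severe) or grade 4 (life-threatening) SAE in 50% percent of subjects", qualified by "that an independent medical monitor and DSMB believe is likely related to active treatment"

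At subject level, "CTCAE grade 4 or 5 hypoglycemia" stops the individual woman.

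On reporting, the same section says "The Primary Investigator will be notified immediately (within 24 hours) of any maternal, fetal, or neonatal deaths". The woman's chart is then copied. It also says "Adverse events will be reported to the Data and Safety Monitoring Board (DSMB"), to be weighed with other interim safety data.

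Section 5.2 (Interim Analysis) says that the DSMB meets monthly and may recommend earlier termination on evidence of harm. It adds "Pre-specified stopping rules for safety will be developed". The Performance Monitoring section (numbered 2.4 in the body, 6.4 in the table of contents) describes the DSMB reports that cover adverse events as semi-annual.

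**The concern.** A set of safety criteria should treat a more severe event at least as seriously as a less severe one. Here the ordering breaks in two places.

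First, fatal hypoglycemia has no standing of its own. It adds one to a count that it shares with non-fatal readings.

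Second, the general SAE criterion covers severe and life-threatening events but not fatal ones. The hypoglycemia table is for maternal events, so two kinds of related death fall outside every written study-level criterion: a maternal death from a cause other than hypoglycemia, and a fetal or neonatal death. The plan foresees such deaths. It requires prompt notice of them and lists neonatal mortality as a secondary outcome (section 4.6.2).

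The trial gives insulin to non-diabetic pregnant women. If a related death occurred, the investigators and the board would find no written statement of what follows at study level, or how soon. Section 5.2 would not help, because it reads as if no safety stopping rules exist yet.

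**Working it through.** **Inputs.** Section 5.1: 144 randomized, 72 per group (144/2 = 72, which agrees). Section 5.2: interim at n=75, so 37 or 38 per arm under 1:1 allocation. Section 4.5: thresholds of more than 33%, more than 50%, and 50%. The documents give no derivation for these thresholds, so there is no plan figure to reproduce. I take every woman allocated to intervention as receiving it.

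**Thresholds as counts.** The smallest count exceeding a fraction f of n is floor(f × n) + 1.

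| Criterion | n | f × n | Count needed |
|---|---|---|---|
| Grade 4 or 5 hypoglycemia, >33% | 72 | 23.76 | 24 (33.3%); 23 is 31.9% |
| Same, interim | 37 | 12.21 | 13 (35.1%) |
| Same, interim | 38 | 12.54 | 13 (34.2%) |
| Same, if 10% are lost | 65 | 21.45 | 22 (33.8%) |
| Grade 3 hypoglycemia, >50% | 72 | 36 | 37 |
| General SAE, 50% of all subjects | 144 | 72 | 72 |
| General SAE, if only the intervention arm is meant | 72 | 36 | 36 |

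If 33% is shorthand for one third, 24/72 is not more than the threshold and the first row becomes 25.

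**Weight of one death.** One fatal hypoglycemia in 72 women is 1/72 = 1.4%. No minimum denominator is stated, so a single case exceeds 33% only while three or fewer women have received the intervention (1/3 = 33.3%, 1/4 = 25%).

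**Chance that the first rule is met at n=72.** This is the exact binomial P(X ≥ 24). The documents give no event rate, so the rates are illustrative assumptions:

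| Assumed true grade 4 or 5 rate | Chance of meeting the rule |
|---|---|
| 10% | 6.4 × 10⁻⁸ |
| 20% | 0.0055 |
| 25% | 0.070 |
| 33% | 0.52 |

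The rule therefore responds only to very frequent events. It cannot serve as a response to a rare fatal one.

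**Events set against the written study-level criteria.**

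| Related event | Counts toward |
|---|---|
| Maternal grade 3 hypoglycemia | >50% rule; general criterion if an SAE |
| Maternal grade 4 hypoglycemia | >33% rule; general criterion if an SAE |
| Maternal death from hypoglycemia | >33% rule only, as one case |
| Other non-fatal grade 3 or 4 SAE | General criterion |
| Maternal death from another cause | None |
| Fetal or neonatal death | None |

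**What is attached to a death.** Section 4.5 gives notice to the Primary Investigator within 24 hours, a copy of the record, and adverse event reporting to the DSMB with no deadline. The subject-level rule has no content for grade 5. Section 5.2 implies monthly board meetings, while Performance Monitoring implies semi-annual adverse event reports. Nothing fixes when the board would consider a death.

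**The case against.** The strongest reply is that deaths are handled by people rather than percentages. A death is notified faster than other adverse events (24 hours against 48 for the form). The board receives adverse events, meets monthly according to section 5.2, and may recommend termination for harm. Section 5.2 also says that stopping will not rest on statistics alone. This stands, and it rules out two stronger readings.

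A reader might infer that a related death would trigger nothing. The documents do not support that: notification, reporting and the board's discretion all apply. What is absent is a pre-specified study-level criterion, action or timing.

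A reader might also infer that the plan tolerates up to 23 deaths, since 23 of 72 does not meet the first rule. That is only the arithmetic limit of one rule at full enrollment with no non-fatal grade 4 events. It ignores individual notification, the board's discretion, and the lower counts needed earlier in recruitment.

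A second reply is that the lists are open-ended, section 5.2 promises further rules, and the DSMB section (3.2.2 in the body) refers to a charter in an appendix that is not in the text I read. A provision on death could exist there. This stands too, and it limits the claim to the protocol text. If the charter has such a provision, 4.5 and 5.2 should point to it.

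A third reply is that grade 5 may be implicit in the general SAE criterion. The text does not say so. Even if it were, a death would then count only toward a 50% threshold.

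**Conclusion.** The point holds as a defect in stated safety criteria, and it should be corrected. Section 4.5 defines grade 5 as death. It then counts a fatal hypoglycemia only as one of the 24 cases needed among 72 women (13 of 37 or 38 at the interim), and leaves grade 5 out of the general SAE criterion. The written criteria therefore count a related non-fatal grade 3 SAE but not a related maternal death from another cause, nor a related fetal or neonatal death.

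The omission does not leave deaths unmonitored. It leaves them without a defined study-level path or timing, in a protocol whose sections disagree on whether safety rules already exist and differ on how often the board sees adverse events.

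The counts assume 72 women receiving the intervention and 33% taken literally. The probabilities rest on assumed event rates. The conclusion about omitted deaths depends on neither; it rests on the wording of 4.5 and is subject to what the charter says.

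**What to change.** Reconcile section 4.5, section 5.2, the Performance Monitoring section and the DSMB charter, so that they agree on which safety stopping rules exist and how often the board receives adverse events. Specifically:

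- Correct the general SAE criterion in 4.5 so that its grade range no longer omits grade 5. This is not enough alone, because a death would still count only toward a 50% threshold.
- Have the sponsor and DSMB state in 4.5, separately from the percentage rules, how and when a maternal, fetal or neonatal death goes to the existing DSMB for review.
- In 5.2, replace the promise of future rules with a reference to that text, and to the charter where it applies.

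The thresholds, the relatedness level and any decision to stop belong to the sponsor and DSMB; none is proposed here. The cost is protocol and charter wording. The board and the 24-hour death notice already exist, and the only operational downside is an occasional unscheduled DSMB review.
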